12. PLANS FOR DISSEMINATING AND COMMUNICATING STUDY RESULTS

As part of the policy of German sickness funds, the results of this study need to be published. The members of the Steering Board will be authors of those publications. The publication strategy includes one full-text manuscript published in a peer-reviewed journal and (optional) one conference abstract/poster presented at a medical congress. Current guidelines and recommendation on good publication practice will be followed (e.g. GPP2 Guidelines [12], STROBE [13]).

ANNEX 1. LIST OF STAND-ALONE DOCUMENTS

None

ANNEX 2. ENCEPP CECKLIST FOR STUDY PROTOCOLS

ENCePP Checklist for Study Protocols (Revision 3)

Adopted by the ENCePP Steering Group on 01/07/2016

The [European Network of Centres for Pharmacoepidemiology and Pharmacovigilance \(ENCePP\)](#) welcomes innovative designs and new methods of research. This Checklist has been developed by ENCePP to stimulate consideration of important principles when designing and writing a pharmacoepidemiological or pharmacovigilance study protocol. The Checklist is intended to promote the quality of such studies, not their uniformity. The user is also referred to the [ENCePP Guide on Methodological Standards in Pharmacoepidemiology](#), which reviews and gives direct electronic access to guidance for research in pharmacoepidemiology and pharmacovigilance.

For each question of the Checklist, the investigator should indicate whether or not it has been addressed in the study protocol. If the answer is "Yes", the section number of the protocol where this issue has been discussed should be specified. It is possible that some questions do not apply to a particular study (for example, in the case of an innovative study design). In this case, the answer 'N/A' (Not Applicable) can be checked and the "Comments" field included for each section should be used to explain why. The "Comments" field can also be used to elaborate on a "No" answer.

This Checklist should be included as an Annex by marketing authorisation holders when submitting the protocol of a non-interventional post-authorisation safety study (PASS) to a regulatory authority (see the [Guidance on the format and content of the protocol of non-interventional post-authorisation safety studies](#)). The Checklist is a supporting document and does not replace the format of the protocol for PASS as recommended in the Guidance and Module VIII of the Good pharmacovigilance practices (GVP).

Study title: Real-world treatment of newly diagnosed COPD patients: A retrospective German claims data analysis

Study reference number: xxxxxxx

Section 1: Milestones	Yes	No	N/A	Section Number
1.1 Does the protocol specify timelines for				
1.1.1 Start of data collection ²³				6
1.1.2 End of data collection ²⁴				6
1.1.3 Study progress report(s)				
1.1.4 Interim progress report(s)				
1.1.5 Registration in the EU PAS register				
1.1.6 Final report of study results.				6

Comments:

Section 2: Research question	Yes	No	N/A	Section Number
2.1 Does the formulation of the research question and objectives clearly explain:				
2.1.1 Why the study is conducted? (e.g. to address an important public health concern, a risk identified in the risk management plan, an emerging safety issue)				8
2.1.2 The objective(s) of the study?				8
2.1.3 The target population? (i.e. population or subgroup to whom the study results are intended to be generalised)				
2.1.4 Which hypothesis(-es) is (are) to be tested?				8
2.1.5 If applicable, that there is no a priori hypothesis?				8

Comments:

Section 3: Study design	Yes	No	N/A	Section Number
3.1 Is the study design described? (e.g. cohort, case-control, cross-sectional, new or alternative design)				9.1
3.2 Does the protocol specify whether the study is based on primary, secondary or combined data collection?				9.3
3.3 Does the protocol specify measures of occurrence? (e.g. incidence rate, absolute risk)				9.7
3.4 Does the protocol specify measure(s) of association? (e.g. relative risk, odds ratio, excess risk, incidence rate ratio, hazard ratio, number needed to harm (NNH) per year)				9.7

²³ Date from which information on the first study is first recorded in the study dataset or, in the case of secondary use of data, the date from which data extraction starts.

²⁴ Date from which the analytical dataset is completely available.

Section 3: Study design	Yes	No	N/A	Section Number
3.5 Does the protocol describe the approach for the collection and reporting of adverse events/adverse reactions? (e.g. adverse events that will not be collected in case of primary data collection)				

Comments:

Section 4: Source and study populations	Yes	No	N/A	Section Number
4.1 Is the source population described?				9.2
4.2 Is the planned study population defined in terms of:				9.2
4.2.1 Study time period?				
4.2.2 Age and sex?				
4.2.3 Country of origin?				
4.2.4 Disease/indication?				
4.2.5 Duration of follow-up?				
4.3 Does the protocol define how the study population will be sampled from the source population? (e.g. event or inclusion/exclusion criteria)				9.2

Comments:

Section 5: Exposure definition and measurement	Yes	No	N/A	Section Number
5.1 Does the protocol describe how the study exposure is defined and measured? (e.g. operational details for defining and categorising exposure, measurement of dose and duration of drug exposure)				
5.2 Does the protocol address the validity of the exposure measurement? (e.g. precision, accuracy, use of validation sub-study)				
5.3 Is exposure classified according to time windows? (e.g. current user, former user, non-use)				
5.4 Is exposure classified based on biological mechanism of action and taking into account the pharmacokinetics and pharmacodynamics of the drug?				

Comments:

This retrospective study is an anonymous data analysis, which is based on prescription data only with regard to drug exposure. So specific exposure measurement will not be done.

Section 6: Outcome definition and measurement	Yes	No	N/ A	Section Number
6.1 Does the protocol specify the primary and secondary (if applicable) outcome(s) to be investigated?				9.3
6.2 Does the protocol describe how the outcomes are defined and measured?				9.3
6.3 Does the protocol address the validity of outcome measurement? (e.g. precision, accuracy, sensitivity, specificity, positive predictive value, prospective or retrospective ascertainment, use of validation sub-study)				9.3
6.4 Does the protocol describe specific endpoints relevant for Health Technology Assessment? (e.g. HRQoL, QALYs, DALYs, health care services utilisation, burden of disease, disease management)				9.3

Comments:

Section 7: Bias	Yes	No	N/ A	Section Number
7.1 Does the protocol describe how confounding will be addressed in the study?				9.7
7.1.1. Does the protocol address confounding by indication if applicable?				
7.2 Does the protocol address:				
7.2.1. Selection biases (e.g. healthy user bias)				9.11
7.2.2. Information biases (e.g. misclassification of exposure and endpoints, time-related bias)				9.11
7.3 Does the protocol address the validity of the study covariates?				9.7

Comments:

Section 8: Effect modification	Yes	No	N/ A	Section Number
8.1 Does the protocol address effect modifiers? (e.g. collection of data on known effect modifiers, sub-group analyses, anticipated direction of effect)				9.7

Comments:

Section 9: Data sources	Yes	No	N/A	Section Number
9.1 Does the protocol describe the data source(s) used in the study for the ascertainment of:				9.4
9.1.1 Exposure? (e.g. pharmacy dispensing, general practice prescribing, claims data, self-report, face-to-face interview)				
9.1.2 Outcomes? (e.g. clinical records, laboratory markers or values, claims data, self-report, patient interview including scales and questionnaires, vital statistics)				

Section 9: Data sources	Yes	No	N/A	Section Number
9.1.3 Covariates?				
9.2 Does the protocol describe the information available from the data source(s) on:				9.3
9.2.1 Exposure? (e.g. date of dispensing, drug quantity, dose, number of days of supply prescription, daily dosage, prescriber)				
9.2.2 Outcomes? (e.g. date of occurrence, multiple event, severity measures related to event)				
9.2.3 Covariates? (e.g. age, sex, clinical and drug use history, co-morbidity, co-medications, lifestyle)				
9.3 Is a coding system described for:				9.3
9.3.1 Exposure? (e.g. WHO Drug Dictionary, Anatomical Therapeutic Chemical (ATC) Classification System)				
9.3.2 Outcomes? (e.g. International Classification of Diseases (ICD)-10, Medical Dictionary for Regulatory Activities (MedDRA))				
9.3.3 Covariates?				
9.4 Is a linkage method between data sources described? (e.g. based on a unique identifier or other)				

Comments:

Section 10: Analysis plan	Yes	No	N/A	Section Number
10.1 Is the choice of statistical techniques described?				9.7
10.2 Are descriptive analyses included?				9.7
10.3 Are stratified analyses included?				
10.4 Does the plan describe methods for adjusting for confounding?				9.7
10.5 Does the plan describe methods for handling missing data?				9.7.2
10.6 Is sample size and/or statistical power estimated?				9.7

Comments:

Section 11: Data management and quality control	Yes	No	N/A	Section Number
11.1 Does the protocol provide information on data storage? (e.g. software and IT environment, database maintenance and anti-fraud protection, archiving)				9.6
11.2 Are methods of quality assurance described?				9.8
11.3 Is there a system in place for independent review of study results?				9.6

Comments:

Section 12: Limitations	Yes	No	N/ A	Section Number
12.1 Does the protocol discuss the impact on the study results of: 12.1.1 Selection bias? 12.1.2 Information bias? 12.1.3 Residual/unmeasured confounding? (e.g. anticipated direction and magnitude of such biases, validation sub-study, use of validation and external data, analytical methods)				9.11/ 9.9
12.2 Does the protocol discuss study feasibility? (e.g. study size, anticipated exposure, duration of follow-up in a cohort study, patient recruitment)				9.5

Comments:

Section 13: Ethical issues	Yes	No	N/ A	Section Number
13.1 Have requirements of Ethics Committee/ Institutional Review Board been described?				10
13.2 Has any outcome of an ethical review procedure been addressed?				
13.3 Have data protection requirements been described?				10

Comments:

Section 14: Amendments and deviations	Yes	No	N/ A	Section Number
14.1 Does the protocol include a section to document amendments and deviations?				5

Comments:

Section 15: Plans for communication of study results	Yes	No	N/ A	Section Number
15.1 Are plans described for communicating study results (e.g. to regulatory authorities)?				12
15.2 Are plans described for disseminating study results externally, including publication?				12

Comments:

Name of the main author of the protocol:

[REDACTED]

Date:

Signature: _____

ANNEX 3. ADDITIONAL INFORMATION

Supplemental Table 1: Variables available for DMP patients

DMP-key	Type	Meaning (German)	Meaning (English)
BETA2.LANG.BEDARF	Boolean ¹	Bedarf einer kurzfristigen langwirksamen Beta-2-Sympathomimetikatherapie	Need for a short therapy with long-acting beta-2-sympathomimetics
BETA2.LANG.DAUER	Boolean ¹	Bedarf einer dauerhaften langwirksamen Beta-2-Sympathomimetikatherapie	Need for a long-lived therapy with long-acting beta-2-sympathomimetics
BETA2_LANG.KEINE	Boolean ¹	Keine Langwirksame Beta-2-Sympathomimetikatherapie indiziert	No therapy with long-acting beta-2-sympathomimetics indicated
BETA2_LANG.KI	Boolean ¹	Langwirksame Beta-2-Sympathomimetikatherapie kontraindiziert	Long-acting beta-2-sympathomimetics contraindicated
ANTI_LANG.BEDARF	Boolean ¹	Bedarf einer kurzfristigen langwirksamen Anticholinergikatherapie	Need for a short therapy with long-acting anticholinergics
ANTI_LANG.DAUER	Boolean ¹	Bedarf einer dauerhaften langwirksamen Anticholinergikatherapie	Need for a long-lived therapy with long-acting anticholinergics
ANTI_LANG.KEINE	Boolean ¹	Keine langwirksame Anticholinergikatherapie indiziert	No anticholinergics indicated
ANTI_LANG.KI	Boolean ¹	Langwirksame Anticholinergikatherapie kontraindiziert	Anticholinergics contraindicated
COP.STATIONAER	Integer ²	Stationäre notfallmäßige Behandlungen wegen COPD seit der letzten Dokumentation (Anzahl)	Emergency inpatient hospitalizations due to COPD since last documentation
COP_EINWEISUNG.JA	Integer ²	COPD-bezogene Über- bzw. Einweisung veranlasst (Anzahl)	COPD-related referral / admission arranged (number of)
COP_EINWEISUNG.NEIN	Integer ²	COPD-bezogene Über- bzw. Einweisung nicht veranlasst (Anzahl)	No COPD-related referral / admission arranged (number of)
COP_EXA	Integer ²	Häufigkeit der COPD Exazerbation	Number of COPD-related hospitalizations
COP_SCHULUNG.NICHT_EMPF	Boolean ¹	Schulung nicht empfohlen	COPD-related training not recommended
COP_SCHULUNG.NM	Boolean ¹	Schulung nicht möglich (Fehlende Schulungskapazität, Krankenhausaufenthalt, private Gründe, ...)	COPD-related training not possible
COP_SCHULUNG.NW	Boolean ¹	Schulung nicht wahrgenommen	COPD-related training not participated
COP_SCHULUNG.OK	Boolean ¹	Empfohlene Schulung(en) wahrgenommen	Participated in recommended COPD-related training

¹Boolean variables represent one of two possible values (e.g. "1" or "0", "yes" or "no").

²Integer variables are variables that must take an integer value (0, 1, 2, ...)

Supplemental Table 2: COPD medications available in the German market

Medication class	Agents	ATC-Codes
SABA	Salbutamol	R03AC02
	Terbutaline	R03AC03
	Fenoterol	R03AC04; R03CC04
	Reprotoerol	R03CC14; R03AC15
LABA	Salmeterol	R03AC12
	Formoterol	R03AC13
	Indacaterol	R03AC18
	Olodaterol	R03AC19
	Bambuterol	R03CC12
	Clenbuterol	R03CC13
LABA-combi	Clenbuterol, combinations	R03CC63
SABA-combi	Fenoterol and sodium cromoglycate	R03AK03
	Salbutamol and sodium	R03AK04
	Reprotoerol and sodium	R03AK05
ICS+LABA	Salmeterol and fluticasone	R03AK06; R03AK61
	Formoterol and budesonide	R03AK07; R03AK28;
	Formoterol and beclometasone	R03AK08; R03AK27;
	Vilanterol and fluticasone furoate	R03AK10
	Formoterol and fluticasone	R03AK11
SABA+SAMA	Fenoterol and ipratropium bromide	R03AL01
	Salbutamol and ipratropium	R03AL02
LABA+LAMA	Vilanterol and umeclidinium	R03AL03
	Indacaterol and glycopyrronium	R03AL04
	Formoterol and aclidinium bromide	R03AL05
	Olodaterol and tiotropium bromide	R03AL06
ICS	Beclometasone	R03BA01; R01AD01
	Budesonide	R03BA02; R01AD05
	Fluticasone	R03BA05; R01AD08
SAMA	Ipratropium bromide	R03BB01; R01AX03
LAMA	Tiotropium bromide	R03BB04
	Aclidinium bromide	R03BB05
	Glycopyrronium bromide	R03BB06
	Umeclidinium	R03BB07
LAMA+LABA+ICS	Glycopyrronium and Formoterol	R03AL09

Medication class	Agents	ATC-Codes
Methylxanthine	Theophylline	R03DA04
	Aminophylline	R03DA05
PDE-4	Roflumilast	R03DX07
Systemic/oral corticosteroids ¹	Prednisolone	R01AD02
	Methylprednisolone	D07AA01; D10AA02;

¹for exacerbations

Supplemental Table 3: Calculation of the Charlson Comorbidity Index (CCI)

No	Comorbidity	Charlson Score	ICD-10 Code
1	Coronary artery disease	1	I20.-, I21.-, I22.-, I23.-, I24.-, I25.-
2	Congestive heart failure	1	I11.-, I50.-
3	Peripheral vascular disease	1	I73.-, I74.-, I77.-
4	Cerebrovascular disease	1	G45.-, G46.-, I6.-
5	Dementia	1	F00.-, F01.-, F02.-, F03.-, G30.-
6	Chronic pulmonary disease	1	J4.-, J6.- w/o J67.-, J68.-, J69.-
7	Connective tissue disorder	1	M05.-, M06.-, M07.-, M08.-, M3.-
8	Peptic ulcer disease	1	K25.-, K26.-, K27.-, K28.-
9	Mild liver disease	1	B18.-, K70.-, K73.-, K75.-
10	Diabetes mellitus without complications	1	E109.-, E119.-, E129.-, E139.-, E149.-
11	Hemiplegia	2	G81.-, G82.-
12	Moderate or severe renal disease	2	N17.-, N18.-, N19.-
13	Diabetes mellitus with end-organ damage	2	E10.-, E11.-, E12.-, E13.-, E14.- w/o [No 10]
14	Tumor without metastases, leukemia, lymphoma, multiple myeloma	2	C% w/o [No 16]
15	Moderate or severe liver disease	3	K72.-, K74.-, I85.-
16	Metastatic solid tumor	6	C77.-, C78.-, C79.-, C80.-
17	AIDS	6	B20.-, B21.-, B22.-, B23.-, B24.-
18	Age factor (was excluded from index)		For each decade \geq 50 years of age, 1 point was added to the score

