[figure not shown]
[figure not shown]
[figure not shown]
[figure not shown]

Protocol for non-interventional studies based on existing data

Document Number:	c30035684-01
BI Study Number:	1237-0092
BI Investigational Product(s):	Not applicable
Title:	Real-world treatment of newly diagnosed COPD patients: A retrospective German claims data analysis
Protocol version identifier:	1.0
Date of last version of protocol:	16 October 2019
PASS:	No
EU PAS register number:	Not applicable
Active substance:	ATC code group R03
Medicinal product:	Not applicable
Product reference:	Not applicable
Procedure number:	Not applicable
Joint PASS:	No
Research question and objectives:	
 A. Description of the real-life drug treatment of patients with incident COPD, including description of treatment sequence/escalation in the first 12/24/36 months after incident diagnosis B. Comparison of initial drug treatment of incident COPD patients with two versions of German treatment guidelines (2012/2018) C. Description of exacerbation frequency (severe exacerbations associated with an inpatient hospitalization) of incident COPD patients in the first 12/24/36 months after incident diagnosis

Proprietary confidential information © 2019 Boehringer Ingelheim International GmbH or one or more of its affiliated companies

	D. Description of health-care resource use (HCRU; including use of oxygen therapy) and direct treatment cost of incident COPD patients in the first 12/24/36 months after incident diagnosis 
Country(-ies) of study:	Germany
Author:	
Marketing authorisation holder(s):	
MAH contact person:	
In case of PASS, add: <EU-QPPV:>	Not applicable
In case of PASS, add: <Signature of EU-QPPV:>	Not applicable
Date:	16 October 2019

Page 1 of 58

Proprietary confidential information

© 2019 Boehringer Ingelheim International GmbH or one or more of its affiliated companies. All rights reserved.
This document may not - in full or in part - be passed on, reproduced, published or otherwise used without prior written permission

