4. ABSTRACT

Name of company: Boehringer Ingelheim			
Name of finished medicinal product: COPD medication of any type			
Name of active ingredient: COPD medication of any type, ATC code R03			
Protocol date: 16 Oct 2019	Study number: 1237-0092	Version/Revision: 1.0	Version/Revision date: Not applicable
Title of study:	Real-world treatment of newly diagnosed COPD patients: A retrospective German claims data analysis		
Rationale and background:	
In terms of COPD drug therapy, the current German COPD guideline (S2) [1, 2] recommends a treatment escalation procedure. For incident COPD patients (for the sake of simplicity, newly diagnosed and so far treatment naïve COPD patients will be referred to as “incident COPD patients” in the following), the German guideline recommends the following:
 
 • No treatment (low symptom burden) • SABA or SAMA • LABA or LAMA or LABA+LAMA. 
All other treatments, particularly combination treatments including ICS¹, are only recommended as escalation therapy.
 
Currently, knowledge on real world treatment of incident COPD patients in Germany is sparse, in particular regarding the frequency of different drug therapy prescriptions and the frequency of early therapy escalation including ICS.
 
This study aims to address this issue by reporting treatment of incident COPD patients in the real world. COPD and treatment associated outcomes, especially severe exacerbations (leading to hospitalization), health-care resource use, and early use of oxygen therapy, will be explored. In addition, real-world treatment of incident COPD patients will be compared to German guidelines, using current 2018 guidelines and 2012 guidelines as framework in two scenario calculations.
		

¹ ICS is recommended by the guideline for COPD patients with an asthmatic component. Based on inclusion/exclusion criteria as applied in this study, these patients will be excluded from analysis.

Name of company: Boehringer Ingelheim			
Name of finished medicinal product: COPD medication of any type			
Name of active ingredient: COPD medication of any type, ATC code R03			
Protocol date: 16 Oct 2019	Study number: 1237-0092	Version/Revision: 1.0	Version/Revision date: Not applicable

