9.2 SETTING

An anonymized dataset from the cooperating sickness funds, which includes all patients with at least one COPD diagnosis, who were insured by this sickness funds for the entire period (01/01/2013 - 30/06/2018) will be available.

A patient will be confirmed as being COPD-incident if specialists documented at least two confirmed outpatient COPD diagnoses (ICD J44.-) and/or at least one inpatient COPD diagnosis (ICD J44.-), without such diagnoses in the previous 12 months and without any COPD prescription in the previous 12 months (Suppl. Table 2).

Specific inclusion criteria can be described as follows:

- All patients should have been covered by the sickness fund for the entire period (01/01/2013-30/06/2018) or, in case a patient deceased after index date, for the time until death
- A patient will be included as an incident COPD patient if either a hospital documented at least one COPD diagnosis (ICD-10 J44.-) or a specialist (pneumologist) documented at least two confirmed COPD diagnoses (above ICD-10 code) in two different quarters; the first of the above diagnoses is defined as index diagnosis; inclusion period is defined as lasting from 01/01/2014 until 30/06/2017

- Patients should not have received any COPD diagnosis (ICD-10 J44.-) or any COPD-associated medication (Suppl. Table 2)⁹ in the 12 months pre-index period
- Patient should have, at date of incident COPD diagnosis (index date), an age of at least 40 years

Patients who received at least one confirmed inpatient asthma diagnosis or two confirmed outpatient diagnoses of asthma (ICD-10: J45.-) by pneumologists after the incident COPD diagnosis (index diagnosis) will be separately observed.

Based on these inclusion/exclusion criteria, the following data sets will be analyzed (Figure 3)¹⁰:

- COPD-FULL DATA: All incident COPD patients with a follow-up of up to 54 months
- COPD-12: All incident COPD patients with a follow-up¹¹ of 12 months since index date
- COPD-24: All incident COPD patients with a follow-up of 24 months since index date
- COPD-36: All incident COPD patients with a follow-up of 36 months since index date
- COPD DMP-FULL DATA: All incident COPD patients with available DMP data (at least one entry during 3 months after index date¹²) and a follow-up of up to 54 months.
- COPD DMP-12: All incident COPD patients with available DMP data (at least one entry during 3 months after index date) and a follow-up of 12 months since index date

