9.3.2 Outcomes

9.3.2.1 Primary outcomes

The primary objective of this study is to describe the real-life drug treatment of patients with incident COPD, including description of treatment sequence/escalation in the first 12/24/36 months after incident diagnosis. This analysis will be based on the following samples:

- COPD-12: All incident COPD patients with a follow-up of 12 months since index date (analysis will be done for the first 12 months of observation)
- COPD-24: All incident COPD patients with a follow-up of 24 months since index date (analysis will be done for the first 24 months of observation)
- COPD-36: All incident COPD patients with a follow-up of 36 months since index date (analysis will be done for the first 36 months of observation)
- COPD FULL DATA: All incident COPD patients. (analysis will be done for the full observation period)
- COPD DMP-12: All incident COPD patients with available DMP data (at least one entry after index date) and a follow-up of 12 months since index date (analysis will be done for the first 12 months of observation)

In this analysis, baseline treatment as well as treatment cascades including mean duration of treatment in the pre-defined follow-up periods will be assessed. Results will be reported as follows:

- Mean number of different agents an observed patient received (per patient year)¹³
- List of most frequently prescribed agents (based on [Suppl. Table 2](#)) including percentage of patients who received these agents
- Longitudinal analysis of treatment patterns/cascades with long-acting bronchodilators and ICS, as described in [Table 2](#). Here, proportion of observed patients whose treatment can be described by the pre-defined treatment patterns will be assessed.

Table 2

Description of treatment patterns/cascades (template for reported outcomes)^{14,15}
(please note: below table might not show all theoretically possible treatment patterns. In the analysis, based on observed treatment patterns, all treatment pattern combinations that were observed in >5% of the patient population will be reported)

Therapy pattern after index date	1st line	2nd line	3rd line	4th line	N (%) of patients
Mono, no switch during follow-up period	LAMA	-	-	-	...
	LABA	-	-	-	...
	ICS	-	-	-	...
Mono, with switch	LAMA	LABA	-	-	...
	LAMA	ICS	-	-	...
	LABA	LAMA			
	LABA	ICS			
	ICS	LABA			
	ICS	LAMA			

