
Description of treatment patterns/cascades (template for reported outcomes)
(please note: below table might not show all theoretically possible treatment patterns. In the analysis, based on observed treatment patterns, all treatment pattern combinations that were observed in >5% of the patient population will be reported)

Therapy pattern after index date	1st line	2nd line	3rd line	4th line	N (%) of patients
Triple therapy, de-escalation during follow-up	LAMA+LABA+ICS	LAMA+LABA LAMA+ICS LABA+ICS			...
Dual therapy, any downgrading during follow-up	LABA+ICS LABA+ICS LAMA+ICS LAMA+ICS LABA+LAMA LABA+LAMA	LABA ICS LAMA ICS LABA LAMA			

Others

For the most common Top-5 treatment cascades, duration of treatment of each line of therapy as well as characteristics of patients that could be assigned to the specific cascades will be reported.

Please note that a specific combination therapy will be assumed to have been prescribed if there was a prescription of a respective combination agent. In case separate agents were prescribed, two scenarios are applied: (1) A combination treatment is assumed to have been prescribed if the respective agents were prescribed at the same day or (2) a combination treatment is assumed to have been prescribed if the respective agents were prescribed within a 21 days window and a similar prescription behavior was repeated at least one additional time (example – assumed LABA+LAMA combination: LABA prescription day 1,

LAMA day 10, LABA day 91, LAMA day 96). Coverage calculation (days covered by a respective treatment pattern) will be based on the defined daily dosage (DDD) of each prescription.

An agent will be considered as discontinued if a supply gap of at least 60 days (sensitivity analysis: 15/30/90 days) is observed.

In an additional Kaplan Meier analysis, time to start of a dual therapy (LAMA+LABA/LABA+ICS/LAMA+ICS) and time to start of a triple therapy (LAMA+LABA+ICS) will be assessed (days from incident diagnosis until first day of triple

therapy). This analysis will be based on the COPD full data sample, i.e. no fixed follow-up period but patient-specific follow-up periods (until end of observational period or until censoring or until date of event, whatever comes first) will be applied.

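### The declared drug scope (ATC group R03) and the closed code list in Supplemental Table 2 do not match in either direction, and no rule covers R03 codes outside the list

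*Combined protocol and SAP*

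**What the plan says.** The title page gives the active substance as "ATC code group R03", and the abstract header as "COPD medication of any type, ATC code R03".

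The operational list is Supplemental Table 2 in Annex 3, headed "Supplemental Table 2: COPD medications available in the German market". Three parts of the plan cite it directly:

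- **Washout (abstract and 9.2):** "Patients should not have received any COPD diagnosis (ICD-10 J44.-) or any COPD-associated medication (Suppl. Table 2"), applied to the 12 months before index. A footnote exempts systemic and oral corticosteroids.
- **Primary outcome (9.3.2.1):** "List of most frequently prescribed agents (based on [Suppl. Table 2").
- **COPD drug use and cost (9.3.2.2, Table 3):** prescriptions, DDDs and drug cost, all for the medications in Supplemental Table 2. Other drugs go to a separate non-COPD item.

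The cascade template (Table 2 in 9.3.2.1) and the guideline rules (9.3.2.2) use the class names LAMA, LABA and ICS and cite no code list. For fixed products, section 9.3.2.1 states that "a specific combination therapy will be assumed to have been prescribed if there was a prescription of a respective combination agent". Separately prescribed agents count as a combination if prescribed on the same day, or repeatedly within a 21-day window. A supply gap of 60 days or more is a discontinuation.

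**The concern.** A scope defined by an ATC group picks up every code in that group. A scope defined by an enumerated list picks up only what was typed in. The plan uses the first as its description and the second as its working rule, and does not say what happens to an R03 code that is in the claims but not on the list. The list also reaches outside R03.

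This affects the results the study is built around: whether the cohort is treatment-naive, how many patients start on ICS, how many reach triple therapy and when, and what COPD drugs cost. Each is a proportion, time or sum that depends on every dispensed product being put in the right class. With an expected cohort above 40,000, sampling error is small, so a modest coding error can exceed the reported confidence interval.

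**Working it through.** **Step 1. Compare scope and list.** Supplemental Table 2 has 49 legible codes. Of these, 42 are in R03 and 7 are not: R01AD01, R01AD05 and R01AD08 (filed as ICS), R01AX03 (filed as SAMA), and R01AD02, D07AA01 and D10AA02 (filed as systemic/oral corticosteroids). The last three are exempt from the washout, so four non-R03 codes matter here. The table has no catch-all row and no ATC version. By contrast, the long-term oxygen footnote to Table 3 names its ICD and OPS versions.

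**Step 2. Find where each rule gets its codes.** The washout, agent list and COPD drug use and cost cite the list. The cascade and guideline rules cite nothing, so either they inherit this list or their classes have no code definition. Section 9.8 plans range and cross-checks on the delivered data but no check of R03 code coverage.

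**Step 3. Follow a patient through the rules as written.**

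- *Only an unlisted R03 product in the pre-index year:* passes the washout and enters as naive.
- *Unlisted ICS at index:* ICS is not flagged, so the patient counts as in line with the 2018 rule. Added to LABA and LAMA, it does not make a triple.
- *Move from listed agents to an unlisted fixed combination:* the separate-agent rules do not apply and the combination product is not recognised. The earlier agents show a gap of 60 days or more, read as a stop instead of an escalation.
- *Only a listed R01AD code, or R01AX03:* excluded if dispensed before index; if dispensed after index, counted as an ICS or SAMA user, with the cost booked as COPD drug cost.

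**Step 4. Scale, on stated assumptions.** The plan's own base reproduces: 26,000 / 40,000 = 65% with a long-acting bronchodilator within 12 months (9.5). The documents give no ICS share and no share of unlisted products. Let p be the true ICS share among the 26,000 and u the share of ICS users whose only ICS is unlisted (both assumed).

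Reported share = p × (1 − u). At p = 30%:

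| u | Reported share | Patients misread (26,000 × p × u) |
|---|---|---|
| 1% | 29.7% | 78 |
| 5% | 28.5% | 390 |
| 10% | 27.0% | 780 |

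Over p = 10-40% and u = 1-10%, the number misread runs from 26,000 × 0.10 × 0.01 = 26 to 26,000 × 0.40 × 0.10 = 1,040.

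For comparison, the 95% CI half-width at p = 30% is 1.96 × √(0.30 × 0.70 / 26,000) = 0.56 percentage points. The bias exceeds this once u is above 0.56 / 30 = 1.9%.

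For the opposite direction, let v be the share of patients without ICS who have only a listed R01AD code after index (assumed). Then reported share = p(1 − u) + (1 − p)v. With p = 30% and u = v = 1%, this is 29.7% + 0.7% = 30.4%, above the true value. The two errors cancel when v = pu / (1 − p) = 0.43u.

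For the washout, if 0.5-5% of the 40,000 had used only an unlisted product before index (assumed), 200 to 2,000 treated patients would count as incident.

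**The case against.** The strongest reply is that nothing in the documents shows a product to be missing. A reader might infer from the numbering that marketed inhaled steroids or a second fixed triple were left out, since R03BA03-04 and R03AL07-08 are skipped. A reader might also note that fenoterol and reproterol carry both R03AC and R03CC codes while salbutamol and terbutaline carry only R03AC. Neither supports that inference: a skipped number does not show that a drug sold in Germany in 2013-2018 has that code, and naming one needs an ATC index that the documents do not reproduce. This part of the reply stands.

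The public text of the table is also damaged. The LAMA+LABA+ICS row names only two components, three rows end in a semicolon, and the abstract's systemic steroid list includes H02AB04, which the table does not show. The single code in the triple row therefore carries no weight as evidence of an omission.

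A reader might further infer that the problem is concentrated in 2018. With index dates uniform over 42 months and follow-up of 12 to 54 months, mean follow-up is 33 months, and the first half of 2018 is 6/33 = 18% of full-sample person-time, ignoring deaths. That is a share of calendar time, not an error rate. Index dates end on 30/06/2017, so the washout, the guideline check at index plus 4 weeks and the early-triple grouping (first 3 months) all end before 2018.

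Two further limits stand. Total drug cost is unaffected, because unlisted drugs move to the non-COPD item. A list narrower than R03 is also not an error in itself, since a study may define COPD drugs more tightly than the ATC group.

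The reply does not remove three facts: the declared scope and the list disagree in both directions, unlisted R03 codes have no handling rule, and the cascade and guideline classes have no other code definition.

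**Conclusion.** The mismatch between scope and list is established from the documents. Misclassification is conditional on unlisted R03 products, or the listed R01 codes, occurring in the claims. Its size and net direction are unknown: unlisted codes lower the ICS and triple counts and admit treated patients, while the R01 codes raise the ICS and SAMA counts and over-exclude at washout. A claim that ICS use is biased downward would go beyond the documents.

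On the assumed range u = 1-10%, the unlisted-ICS route alone would move a true 30% share to 29.7-27.0%. COPD drug cost can be misallocated; total drug cost cannot. The point should be settled before extraction because the remedy is nearly free and protects the naive-cohort, ICS and triple results whichever way the error runs.

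**What to change.** Replace the closed list with one component-based map:

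1. Tabulate every R03 code present in the claims for the full data period, including any added quarters, and check the list against the ATC version in force for those years.
2. Assign each code to a class, or combination of classes, by its components.
3. Use that map for the washout, the Table 2 cascades, the guideline rules and COPD drug use and cost, and cite it in each section.
4. Report any R03 code left unassigned, with its number of users.
5. Justify R01AD01, R01AD05 and R01AD08 in the ICS row and R01AX03 in the SAMA row, or remove them.

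If the sponsor prefers a list narrower than R03, the title page and abstract should say so, and the exclusion of the remaining R03 codes should be explained.

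The cost is one mapping table and a small change in the number passing the washout. The data set already carries ATC codes (9.1, Table 1), so no new data are needed.
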